8.3.1 Hy's Law

Cases where a patient shows elevations in liver biochemistry may require further evaluation and occurrences of AST or ALT $\geq 3 \times$ ULN together with total bilirubin $\geq 2 \times$ ULN may need to be reported as SAEs.

8.4 SAEs or Serious SARs

8.4.1 Timing

After informed consent but prior to initiation of study medications, only SAEs caused by a protocol-mandated intervention will be collected (e.g. SAEs related to invasive procedures such as biopsies, medication washout).

For any other experience or condition that meets the definition of an SAE or a serious SAR, recording of the event must begin from day 1 of study treatment and continue through the 90 day follow-up period after treatment is discontinued.

8.4.2 Documentation and Notification

SAEs or Serious SARs must be recorded in the SAE console within OncoreTM for that patient within 24 hours of learning of its occurrence. Additionally, the Multicenter Project Manager must also be notified via email of all SAEs within 24 hours of learning of its occurrence.

8.5 Adverse Event Reporting

8.5.1 IRB Reporting Requirements:

UNC:

- The UNC-IRB will be notified of all SAEs that qualify as an Unanticipated Problem as per the UNC IRB Policies using the IRB's web-based reporting

system within 7 days of the Investigator becoming aware of the problem. Please note, these events must be reported to the sponsor within 24 hours of learning of the occurrence.

Multicenter sites:

- For multicenter sites using a local IRB of record, please submit adverse events per local IRB policy.

Pregnancy

Pregnancies and suspected pregnancies (including a positive pregnancy test regardless of age or disease state) of a female subject occurring while the subject is on study, or within 90 days of the subject's last dose of study should be recorded as important medical events. The patient is to be discontinued immediately from the study.

For multicenter sites, the pregnancy, suspected pregnancy, or positive pregnancy test must be reported to the Multicenter Project Manager immediately (within 24 hours) via email (preferable) to [contact] or facsimile to [contact]. The Multicenter Project Manager will then report the event to the Funding Source (see requirements below). The female subject should be referred to an obstetrician-gynecologist, preferably one experienced in reproductive toxicity for further evaluation and counseling.

The Investigator will follow the female subject until completion of the pregnancy, and must document the outcome of the pregnancy (either normal or abnormal outcome) and report the condition of the fetus or newborn to the Multicenter Project Manager. If the outcome of the pregnancy was abnormal (e.g., spontaneous or therapeutic abortion), the Investigator should report the abnormal outcome as an AE. If the abnormal outcome meets any of the serious criteria, it must be reported as an SAE.

8.5.2 AstraZeneca Reporting Requirements:

AstraZeneca/MedImmune retains the right to request additional information for any patient with ongoing AE(s)/SAE(s) at the end of the study, if judged necessary.

All SAEs will be reported, whether or not considered causally related to the investigational product, or to the study procedure(s). The reporting period for SAEs is the period immediately following the time that written informed consent is obtained through 90 days after the last dose of durvalumab or until the initiation of alternative anticancer therapy. The investigator and/or Sponsor are responsible for informing the Ethics Committee and/or the Regulatory Authority of the SAE as per local requirements.

The investigator and/or sponsor must inform the FDA, via a MedWatch/AdEERS form, of any serious or unexpected adverse events that occur in accordance with

the reporting obligations of 21 CFR 312.32, and will concurrently forward all such reports to AstraZeneca. A copy of the MedWatch/AdEERs report must be emailed to AstraZeneca at the time the event is reported to the FDA. It is the responsibility of the sponsor to compile all necessary information and ensure that the FDA receives a report according to the FDA reporting requirement timelines and to ensure that these reports are also submitted to AstraZeneca at the same time.

* A *cover page* should accompany the *MedWatch/AdEERs* form indicating the following:

- “Notification from an Investigator Sponsored Study”
- The investigator IND number assigned by the FDA
- The investigator’s name and address
- The trial name/title and AstraZeneca ISS reference number (ESR 17-12741)

* Sponsor must also indicate, either in the SAE report or the cover page, the *causality* of events *in relation to all study medications* and if the SAE is *related to disease progression*, as determined by the principal investigator.

* *Send SAE report and accompanying cover page by way of email to AstraZeneca’s designated mailbox:*

[contact]

If a non-serious AE becomes serious, this and other relevant follow-up information must also be provided to AstraZeneca and the FDA.

Serious adverse events that do not require expedited reporting to the FDA still need to be reported to AstraZeneca preferably using the MedDRA coding language for serious adverse events. This information should be reported on a monthly basis and under no circumstance less frequently than quarterly.

8.5.2.1 Reporting of deaths to AstraZeneca

All deaths that occur during the study, or within the protocol-defined 90-day post-last dose of durvalumab safety follow-up period must be reported to AstraZeneca as follows:

- Death that is clearly the result of disease progression should be documented but should not be reported as an SAE.
- Where death is not due (or not clearly due) to progression of the disease under study, the AE causing the death must be reported to AstraZeneca as a SAE within **24 hours**. The report should contain a comment regarding the co-involvement of progression of disease, if appropriate, and should assign main and contributory causes of death.
- Deaths with an unknown cause should always be reported as a SAE.

8.5.2.2 Overdose

Use of durvalumab in doses in excess of that specified in the protocol is considered to be an overdose. There is currently no specific treatment in the event

of overdose of durvalumab b and possible symptoms of overdose are not established.

- An overdose with associated AEs will be recorded as the AE diagnosis or symptoms in the relevant AE modules of the eCRF and in the Overdose eCRF module.
- An overdose without associated symptoms will only be reported in the Overdose eCRF module.

If an overdose of an AstraZeneca IP occurs in the course of the study, then the Investigator or other site personnel will inform appropriate AstraZeneca representatives immediately, or **no later than 24 hours** of when he or she becomes aware of it.

The designated AstraZeneca representative will work with the Investigator to ensure that all relevant information is provided to the AstraZeneca Patient Safety data entry site.

For overdoses associated with an SAE, the standard reporting timelines apply. For other overdoses, reporting must occur within 30 days.

8.5.2.3 Pregnancy

All pregnancies and outcomes of pregnancy should be reported to AstraZeneca except for pregnancy discovered before the study patient has received any study drugs.

8.5.2.4 Maternal exposure

If a patient becomes pregnant during the course of the study, the IP should be discontinued immediately.

Pregnancy itself is not regarded as an AE unless there is a suspicion that the IP under study may have interfered with the effectiveness of a contraceptive medication. Congenital abnormalities or birth defects and spontaneous miscarriages should be reported and handled as SAEs. Elective abortions without complications should not be handled as AEs. The outcome of all pregnancies (spontaneous miscarriage, elective termination, ectopic pregnancy, normal birth, or congenital abnormality) should be followed up and documented even if the patient was discontinued from the study.

If any pregnancy occurs in the course of the study, then the Investigator or other site personnel should inform the appropriate AstraZeneca representatives within 1 day, i.e., immediately, but **no later than 24 hours** of when he or she becomes aware of it.

The designated AstraZeneca representative will work with the Investigator to ensure that all relevant information is provided to the AstraZeneca Patient Safety

data entry site within 1 to 5 calendar days for SAEs and within 30 days for all other pregnancies.

The same timelines apply when outcome information is available.

8.5.2.5 Paternal exposure

Male patients should refrain from fathering a child or donating sperm during the study and for 90 days after the last dose of durvalumab.

Pregnancy of the patient's partner is not considered to be an AE. However, the outcome of all pregnancies (spontaneous miscarriage, elective termination, ectopic pregnancy, normal birth, or congenital abnormality) occurring from 90 days after the last dose of durvalumab monotherapy, should, if possible, be followed up and documented.

Where a report of pregnancy is received, prior to obtaining information about the pregnancy, the Investigator must obtain the consent of the patient's partner. Therefore, the local study team should adopt the generic ICF template in line with local procedures and submit it to the relevant Ethics Committees (ECs)/Institutional Review Boards (IRBs) prior to use.

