4.1.8 Women of childbearing potential (WOCBP) must have a negative serum pregnancy test within 7 days prior to treatment. NOTE: Females are considered of child bearing potential unless they are surgically sterile (have undergone a hysterectomy, bilateral tubal ligation, or bilateral oophorectomy) or they are naturally postmenopausal for at least 12 consecutive months. Documentation of postmenopausal status must be provided.

4.1.9 WOCBP must be willing to abstain from heterosexual activity or to use at least 1 highly effective method of contraception from the time of informed consent until 90 days after durvalumab monotherapy treatment is discontinued (whichever is longer).

See section 5.6 of the protocol for additional details on contraception requirements for WOCBP and male participants in this trial.

4.1.10 Male patients with female partners must have had a prior vasectomy or agree to use an adequate method of contraception (i.e., double barrier method: condom plus

spermicidal agent) starting with the first dose of study therapy through 90 days after durvalumab monotherapy is discontinued.

4.1.11 Subjects must be willing and able to comply with study procedures based on the judgment of the investigator or protocol designee.

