5.6 Contraception Requirements

Female patient of childbearing potential

Females of childbearing potential who are sexually active with a non-sterilized male partner must use at least 1 highly effective method of contraception (see Table below) from the time of screening and must agree to continue using such precautions for 90 days after the last dose of durvalumab monotherapy. Non-sterilized male partners of a female patient must use male condom plus spermicide throughout this period. Cessation of birth control after this point should be discussed with a responsible physician. Not engaging in sexual activity for the total duration of the drug treatment and the drug washout period is an acceptable practice; however, periodic abstinence, the rhythm method, and the withdrawal method are not acceptable methods of birth control. Female patients should also refrain from breastfeeding throughout this period.

Male patients with a female partner of childbearing potential:

Non-sterilized males who are sexually active with a female partner of childbearing potential must use a male condom plus spermicide from screening through 90 days after receipt of the final dose of durvalumab monotherapy. Not engaging in sexual activity is an acceptable practice; however, occasional abstinence, the rhythm method, and the withdrawal method are not acceptable methods of contraception. Male patients should refrain from sperm donation throughout this period.

Female partners (of childbearing potential) of male patients must also use a highly effective method of contraception throughout this period (Table 1).

Females of childbearing potential are defined as:

Those who are not surgically sterile (i.e., bilateral tubal ligation, bilateral oophorectomy, or complete hysterectomy) or post-menopausal.

Women will be considered post-menopausal if they have been amenorrheic for 12 months without an alternative medical cause. The following age-specific requirements apply:

- Women <50 years of age would be considered post-menopausal if they have been amenorrheic for 12 months or more following cessation of exogenous hormonal treatments and if they have luteinizing hormone and follicle-stimulating hormone levels in the post-menopausal range for the institution or underwent surgical sterilization (bilateral oophorectomy or hysterectomy).

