8.1.4 Serious AE or SAR

A serious adverse event is an AE occurring during any study phase (i.e., screening, run-in, treatment, wash-out, follow-up), at any dose of the study drug: An AE or SAR is considered serious if, in the view of either the investigator or sponsor, it results in any of the following outcomes:

- Death;
- Is life-threatening (places the subject at immediate risk of death from the event as it occurred);
- Requires inpatient hospitalization (>24 hours) or prolongation of existing hospitalization;*
- Results in congenital anomaly/birth defect;
- Results in a persistent or significant incapacity or substantial disruption of the ability to conduct normal life functions;
- Important medical events that may not result in death, be life-threatening, or require hospitalization may be considered a serious adverse drug experience when, based upon appropriate medical judgment, they may jeopardize the patient or subject and may require medical or surgical intervention to prevent one of the outcomes listed in the definition. For reporting purposes, also consider the occurrences of pregnancy as an event which must be reported as an important medical event.

*Hospitalization for anticipated or protocol specified procedures such as administration of chemotherapy, central line insertion, metastasis interventional therapy, resection of primary tumor, or elective surgery, will not be considered serious adverse events.

The causality of SAEs (their relationship to all study treatment/procedures) will be assessed by the investigator(s) and communicated to AstraZeneca

Pregnancy that occurs within 90 days of the last dose of durvalumab must also be reported as an important medical event.

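### Section 8.5.2.5 sets partner-pregnancy outcome follow-up to start where the section's own paternal risk period ends; the window needs to be reconciled

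*Combined protocol and SAP*

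**What the plan says.** Section 8.5.2.5 opens with the restriction on male patients: "Male patients should refrain from fathering a child or donating sperm during the study and for 90 days after the last dose of durvalumab". Its second paragraph says that a partner's pregnancy is not an adverse event, but that the outcomes of partner pregnancies "occurring from 90 days after the last dose of durvalumab monotherapy" should be followed up and documented if possible. No end date is given. A third paragraph deals with obtaining the partner's consent once a pregnancy has been reported, and sets no time window.

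The general rule is in Section 8.5.2.3: "All pregnancies and outcomes of pregnancy should be reported to AstraZeneca except for pregnancy discovered before the study patient has received any study drugs". It does not mention partners.

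Other sections use the same 90-day mark as an end point:

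- Section 5.6: non-sterilized men with a partner of childbearing potential "must use a male condom plus spermicide from screening through 90 days after receipt of the final dose of durvalumab monotherapy".
- Inclusion criterion 4.1.10: male contraception "starting with the first dose of study therapy through 90 days after durvalumab monotherapy is discontinued".
- Section 8.1.4: "Pregnancy that occurs within 90 days of the last dose of durvalumab must also be reported as an important medical event".
- Section 8.5.1: pregnancies "of a female subject occurring while the subject is on study, or within 90 days of the" last dose are recorded as important medical events.

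**The concern.** Outcome follow-up of partner pregnancies exists to learn what happens when the father has been exposed to the drug. One would expect the follow-up window to match the period in which the protocol tells him not to father a child. As written, the two windows in Section 8.5.2.5 meet at day 90 after the last dose and run in opposite directions: the restriction stops there and the follow-up starts there.

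A site with a partner pregnancy during treatment will turn to this section, because it is the only one that sets outcome follow-up for partners. Taken at its word, the section tells the site to document outcomes of later pregnancies and is silent on those in the restricted period. What is at stake is the completeness of exposure-pregnancy information, and possibly the wording of the partner consent form that the same section asks sites to submit for ethics review.

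**Working it through.** There is no stated figure to reproduce. The check is a comparison of windows, followed by one piece of arithmetic on the dosing schedule.

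**Windows side by side**

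| Section | Subject of the rule | Start | End |
|---|---|---|---|
| 8.5.2.5, first sentence | Fathering a child, sperm donation | During the study | 90 days after last dose |
| 8.5.2.5, second paragraph | Outcome follow-up of partner pregnancies | 90 days after last dose | None given |
| 4.1.10 | Male contraception | First dose | 90 days after discontinuation |
| 5.6 | Male contraception | Screening | 90 days after final dose |
| 4.2.15 | Birth control, both sexes | Screening | 90 days after last dose |
| 8.1.4 | Pregnancy as important medical event | Not stated | 90 days after last dose |
| 8.5.1 | Pregnancy of a female subject | On study | 90 days after last dose |
| 8.5.2.3 | All pregnancies and outcomes, to the company | Excludes those discovered before any study drug | None given |

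The second row is the only one that uses the 90-day mark as a start. It conflicts with the sentence above it and with the direction of every other 90-day window in the table. A start point may have dropped out of the phrase, but the documents do not show this.

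**Length of the stretch before follow-up begins**

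Input: Section 5.2.1 gives durvalumab every 3 weeks for cycles 1 to 3 and every 4 weeks for cycles 4 to 6. Assume all six doses are given without delay, and count the first dose as day 0.

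- Doses 1 to 4: days 0, 21, 42 and 63 (3 × 21 = 63).
- Doses 5 and 6: days 91 and 119 (63 + 2 × 28 = 119).
- Follow-up as written begins on day 119 + 90 = 209.
- In weeks: 209 / 7 = 29.9.

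Early discontinuation shortens this stretch and dose delays lengthen it. Counting from screening, as Section 5.6 does, also lengthens it.

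**What falls outside the literal window**

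The text says *occurring*, not conceived.

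- A pregnancy that begins and ends before day 90 after the last dose is outside on any reading.
- One that begins earlier and is still ongoing at that point can be argued to be inside.
- One that begins later is inside.

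**Whether another rule fills the gap**

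- Section 8.5.2.3 is broad enough in its words to take in partners and covers outcomes. However, it does not name partners, and its one exception is framed around the study patient.
- Section 8.5.2.4 speaks of all pregnancies, but under the heading of maternal exposure and for a patient who becomes pregnant.
- Section 8.5.1 is limited to female subjects.
- Section 8.1.4 is not limited by sex, but it concerns reporting the event, not following it to outcome.

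Section 8.5.2.3 is therefore the only candidate for collecting these outcomes, and its scope is not stated clearly enough to settle the matter.

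**The case against.** The strongest reply is that nothing need be lost. Section 8.5.2.3 comes just before the maternal and paternal subsections, asks for "All pregnancies and outcomes of pregnancy should be reported to AstraZeneca", and has a single exception, which does not concern partners. An outcome cannot be reported unless someone obtains it. No section says that 8.5.2.5 overrides 8.5.2.3, and 8.5.2.5 does not forbid follow-up of earlier partner pregnancies; it adds a request qualified by feasibility. A site that follows both sections could still report exposed partner pregnancies and their outcomes. This stands, with the limit that coverage of partners under 8.5.2.3 is arguable and not explicit.

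Three further points also stand. The word *occurring* narrows the set that is clearly excluded. The 209 days measure calendar time, not affected pregnancies: the trial plans 18 subjects, the documents give no sex split and no partner-pregnancy rate, and male patients must use contraception. The consistent direction of the other windows also suggests a drafting slip and not a deliberate choice.

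What the reply does not remove is the contradiction. On the broadest reading of 8.5.2.3, the two sections still give different scopes for the same event, and 8.5.2.5 still disagrees with its own first sentence.

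**Conclusion.** Section 8.5.2.5 is internally inconsistent. Its partner follow-up window begins where its paternal risk period ends, and it has no end date. Read literally, it omits at least partner pregnancies that begin and end within about 209 days (29.9 weeks) of first dose, assuming six doses without delay.

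A reader might go further in three ways that the documents do not support:

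- **That outcomes of exposed partner pregnancies will be lost.** This holds only if 8.5.2.3 does not cover partners, which the text leaves open. Loss is possible, not certain.
- **That every pregnancy conceived in the risk period is excluded.** The text does not speak of conception, and a pregnancy still ongoing at day 90 may be covered.
- **That 209 days is the whole stated risk period.** The section refers to the study and not to the first dose, and Section 5.6 starts male contraception at screening, so 209 days is only the part counted from first dose.

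Severity is low. The point concerns safety reporting alone and has no bearing on disease-free survival, the toxicity endpoints, the sample size or the analysis.

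**What to change.** Reconcile the follow-up window in the second paragraph of Section 8.5.2.5 with the period in its first sentence and with Sections 4.1.10, 5.6, 8.1.4, 8.5.1 and 8.5.2.3. Give the window both a start and an end. Sections 4.1.10 and 5.6 start male contraception at different times (first dose and screening), so the sponsor should settle which starting point the follow-up window refers to. State in 8.5.2.3 whether it covers pregnancies of patients' partners, and check any partner consent form already in use against the corrected wording.

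The cost is one phrase in 8.5.2.5 and one clarifying sentence in 8.5.2.3, which can go into the next amendment. No new assessments and no change to the analysis are needed.

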8.5.2.6 Medication error

For the purposes of this clinical study a medication error is an unintended failure or mistake in the treatment process for an AstraZeneca study drug that either causes harm to the patient or has the potential to cause harm to the patient. A medication error is not lack of efficacy of the drug, but rather a human or process related failure while the drug is in control of the study site staff or patient.

Medication error includes situations where an error:

- Occurred
- Was identified and intercepted before the patient received the drug
- Did not occur, but circumstances were recognized that could have led to an error
- Examples of events to be reported in clinical studies as medication errors:
 - Drug name confusion
 - Dispensing error e.g. medication prepared incorrectly, even if it was not actually given to the patient
 - Drug not administered as indicated, for example, wrong route or wrong site of administration
 - Drug not taken as indicated e.g. tablet dissolved in water when it should be taken as a solid tablet
 - Drug not stored as instructed e.g. kept in the fridge when it should be at room temperature
 - Wrong patient received the medication
 - Wrong drug administered to patient

- Examples of events that do not require reporting as medication errors in clinical studies:
 - Patient accidentally missed drug dose(s) e.g. forgot to take medication
 - Accidental overdose (will be captured as an overdose)
 - Patient failed to return unused medication or empty packaging
 - Errors related to background and rescue medication, or standard of care medication in open label studies, even if an AstraZeneca product
- Medication errors are not regarded as AEs but AEs may occur as a consequence of the medication error.

If a medication error occurs in the course of the study, then the Investigator or other site personnel informs the appropriate AstraZeneca representatives within 1 day i.e., immediately but **no later than 24 hours** of when he or she becomes aware of it.

The designated AstraZeneca representative works with the Investigator to ensure that all relevant information is completed within 1 or 5 calendar days if there is an SAE associated with the medication error and within 30 days for all other medication errors.

8.5.3 FDA Expedited Reporting requirements for studies conducted under an IND:

A sponsor must report any suspected adverse reaction (SARs) that is both serious and unexpected to the FDA. Please refer to Section 8.1.2 for the definition of an SAR.

The sponsor must submit each IND safety report on FDA Form 3500A.

Timing

FDA must be notified of potential serious risks within 15 calendar days after the sponsor determines the event requires reporting. FDA must be notified of unexpected fatal or life-threatening suspected adverse reactions as soon as possible but in no case later than 7 calendar days after the sponsor's initial receipt of the information. The sponsor must be notified of the SAE by the investigator within 24 hours of the event and thus the Multicenter Project Manager must be notified within 24 hours of the event. If the results of a sponsor's investigation show that an adverse event not initially determined to be reportable is reportable, the sponsor must report such suspected adverse reaction in an IND safety report as soon as possible, but in no case later than 15 calendar days after the determination is made.

Follow-up

The sponsor must promptly investigate all safety information it receives. Relevant follow-up information to an IND safety report must be submitted as soon as the information is available.

Notification of Investigators

The sponsor must notify all participating investigators (i.e., all investigators to whom the sponsor is providing drug under its INDs or under any investigator's IND) in an IND safety report of potential serious risks, from clinical trials or any other source, as soon as possible, but in no case later than 15 calendar days after the sponsor determines that the information qualifies for reporting.

Process

If the sponsor deems that an event is both a serious adverse reaction (SAR) AND unexpected, it must also (in addition to OnCore™) be recorded on the MedWatch Form 3500A as per 21 CFR 312.32. Unexpected adverse events or adverse reaction refers to an event or reaction that is not listed in the investigator's brochure or is not listed at the specificity or severity that has been observed; or if an investigator's brochure is not required or available, is not consistent with the risk information described in the general investigation plan or elsewhere in the current IND application.

The MedWatch form should be submitted on MedWatch by the study coordinator.

The MedWatch form should be emailed faxed to the Multicenter Project Manager at [contact] or [contact] along with supporting documentation defining the event and causality. The Multicenter Project Manager will then send the report to the Funding Source. The MedWatch 3500A form can be accessed at:

<http://www.fda.gov/Safety/MedWatch/HowToReport/DownloadForms/default.htm>

(Please be sure and access form 3500A, and not form 3500).

The Multicenter Project Manager will also be responsible for informing each multicenter site of all serious and unexpected SARs reported to the FDA as soon as possible.

Additional Reporting Requirements

The following additional items must be reported via IND safety report:

- *Findings from other studies.* The sponsor must report any findings from epidemiological studies, pooled analysis of multiple studies, or clinical studies, whether or not conducted under an IND, and whether or not conducted by the sponsor, that suggest a significant risk to humans exposed to the drug.
- *Findings from animal or in vitro testing.* The sponsor must report any findings from animal or *in vitro* testing, whether or not conducted by the

sponsor, that suggest a significant risk in humans exposed to the drug, such as reports of mutagenicity, teratogenicity, or carcinogenicity, or reports of significant organ toxicity at or near the expected human exposure.

- *Increased rate of occurrence of serious suspected adverse reactions.*

Additional Guidance

Please refer to 21CFR312.32 and “Guidance for Industry and Investigators: Safety Reporting Requirements for INDs and BA/BE Studies” for additional information and reporting requirements. All IND Safety Reports will be submitted in accordance with these regulations/guidances.

